held device that instantly analyzes exhaled air for NO concentration. Children will be asked to first fully exhale and then to take a fast and deep inhalation through a disposable mouthpiece attached to the device. Then, we will ask children to exhale slowly and steadily through the mouthpiece. If done correctly, a reading will appear on the screen which will be recorded manually. FeNO will be measured 3 times, once at the baseline visit, at 4-month follow-up, and then again at the end of the school year. Some children may have difficulty with this procedure; we will only include data for children who are able to perform the procedure accurately.

Secondary Smoke Exposure: Saliva Sample Collection for Measurement of Cotinine:

Exposure to secondhand smoke will be assessed by both interview survey and cotinine measurements. At the beginning and the end of the program, a member of the research team will collect salivary fluid samples from each child using the Sorbette fluid specimen collection device, which consists of a small sterile swab mounted on the end of a 5.5 cm plastic handle. Collection will be made according to a standard protocol developed for use with children. Salivary samples will be stored frozen and shipped via courier to Salimetrics, LLC in State College, PA for analysis. The cotinine results will be recorded as an outcome measure, and will be available to families only by request. However, all families will receive resources on how to stop smoking and prevent smoke exposure.

6. Compensation

Each participating parent will be paid \$20 after completion of the baseline assessment. Subjects will also be mailed \$20 after each of the telephone follow-up surveys and \$50 after the final follow-up survey. Total payment will be no more than \$130. Payment to participants will be in the form of a Wegman's grocery store gift certificate.

Healthcare providers who complete an evaluation at the end of the program will be mailed a \$5 Starbucks gift card to thank them for their time.

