Potential benefits for participants of the randomized trial exist for both groups of children (SB-TEAM and eUC). The goal is for children in the SB-TEAM group to have improved symptom assessment, adherence

to preventive medications, and appropriate tailoring of therapy, thus they may experience less morbidity from asthma. Although children in the eUC group will not be receiving medication through school or telemedicine asthma visits, we will prompt their PCP to provide guideline based asthma care including prescription of the appropriate preventive medications and will provide regular reminders to PCPs and caregivers to care for the child's asthma. Improved asthma management should result in reduced morbidity for these children. Since the medications used in this study are safe and effective at the doses administered, and are strongly recommended by the national asthma guidelines, we anticipate that the intervention benefits will outweigh the minimal risk of participation.

11. Analysis

Sample Size:

This study is designed to have adequate power to detect the smallest clinically significant difference in mean SFDs post-intervention between the intervention and enhanced usual care groups. Based on our previous data, we estimate the pooled standard deviation of SFD at 2.8 and within-subject correlation at 0.3. Power was calculated for the intervention effect on SFD with at least two assessments for each subject. We anticipate <15% attrition, as attrition was minimal (<10%) in the prior study, and therefore plan to enroll 400 children. With a final sample of 336, we will have 90% power to detect a difference of 0.8 symptom-free days or greater per 2-wk. period. This difference is supported by our prior data, and would justify continuing the intervention. There are more than 11,000 students in pre-k through 4th grade in the RCSD and at least 6,600 entering kindergarteners in a 3 year period. Conservatively assuming an asthma prevalence of 9%, more than 1,584 students have asthma, and approximately ½ of these students (792) have persistent asthma. In our prior study, we enrolled 74% of eligible subjects. A conservative estimate would allow us to enroll 120 subjects/year (60%), which is more than adequate to meet our sample size.

Primary Analysis:

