The primary analysis of this study aims to assess the effectiveness of the SB-TEAM intervention in reducing asthma morbidity (including symptom-free days post-intervention (follow-ups at 4 mo, 6mo and final) as the primary outcome) compared to an enhanced usual care comparison group in school age children with persistent asthma. We will follow subjects prospectively throughout the school year for clinical outcomes (symptoms, asthma control, health care use), functional outcomes (absenteeism, quality of life), and airway inflammation (FeNO). We will use graphical and numerical summaries to describe the outcomes at each assessment point. If distributional assumptions associated with a particular statistical procedure are violated, appropriate transformations will be made or non-parametric alternatives will be used. In accordance with the intention-to-treat principle, all randomized subjects will be analyzed within the group to which they were assigned; minimal crossover is expected. Hypothesis-driven comparisons will be made to control the family-wise type I error rate at 0.05 (two-sided) for the primary hypothesis.

We will determine whether there are important differences at baseline despite randomization between the SB-TEAM and eUC groups in demographics and background characteristics (age, race, ethnicity, insurance, caretaker education), depression, and cotinine. This will include t-tests (or Wilcoxon Rank Sum test) for continuous variables and chi-square (or Fisher's Exact) tests for discrete variables. These comparisons will enable the identification of control variables for use in analyses evaluating treatment effect.

To test for differences between the SB-TEAM and eUC groups on clinical and functional outcomes at the primary time point, bivariate comparisons will be made using t-tests for continuous variables (number of symptom-free days (SFD), symptom nights, rescue medication use, days absent, quality of life, FeNO,

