and ACT scores), and chi-square tests for discrete variables (acute visits, hospitalizations). In addition, the time-course of treatment response during the follow-up period will be evaluated using a linear mixed model with the primary outcome, SFD at post-intervention, as the response, and treatment condition, treatment by time interaction as independent variables. We will model the repeated assessment post-intervention and assess post treatment effects as well as maintenance gain during the period using appropriate linear contrasts. The analysis will be controlled for baseline symptoms, and variables that are found to differentiate between groups at baseline. The treatment effect will be regarded as fixed and the subjects will be modeled as random effect, with an appropriate variance covariance structure specified. Secondary continuous outcomes will be analyzed in a similar manner. Discrete outcomes will be analyzed by fitting Generalized Estimating Equation model. Appropriate link functions and response probability distributions will be specified.

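### The plan names no single primary test of symptom-free days: it gives a t-test at an undefined time point and a mixed model with no contrast labelled primary

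*Combined protocol and SAP*

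**What the plan says.** All of this stands in section 11 (Analysis) of the combined protocol and SAP, except the FeNO schedule, which is in section 5 (Measures).

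- **Sample Size.** The power basis is a repeated-assessment effect: "Power was calculated for the intervention effect on SFD with at least two assessments for each subject". With SD 2.8 and within-subject correlation 0.3, the result is "With a final sample of 336, we will have 90% power to detect a difference of 0.8 symptom-free days or greater" per two-week period.
- **Primary Analysis, outcome.** The outcome is "symptom-free days post-intervention (follow-ups at 4 mo, 6mo and final) as the primary outcome". The plan undertakes to "control the family-wise type I error rate at 0.05 (two-sided) for the primary hypothesis".
- **Primary Analysis, t-tests.** Group differences are to be tested "at the primary time point, bivariate comparisons will be made using t-tests for continuous variables (number of symptom-free days (SFD" and six further continuous measures, with chi-square tests for the discrete ones. The time point is singular and is not defined anywhere.
- **Primary Analysis, mixed model.** The next sentence reads: "In addition, the time-course of treatment response during the follow-up period will be evaluated using a linear mixed model with the primary outcome", SFD, as the response. Then: "We will model the repeated assessment post-intervention and assess post treatment effects as well as maintenance gain during the period using appropriate linear contrasts". The model is adjusted for baseline symptoms and for variables that differ between groups at baseline. No contrast is called primary.
- **Primary Analysis, missing data.** The paragraph on the intention-to-treat primary analyses discusses the validity of inference for GEE and the linear mixed model. It does not mention the t-test.
- **Section 5, FeNO.** "FeNO will be measured 3 times, once at the baseline visit, at 4-month follow-up, and then again at the end of the school year". FeNO is one of the measures in the t-test sentence.

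**The concern.** Control of the error rate for a primary hypothesis needs one identified test, and here there are several candidates: an unadjusted t-test at 4 months, at 6 months or at the final visit, a mixed-model effect averaged over visits, and model contrasts for post-treatment effect or maintenance. Two analysts who follow the text faithfully could report different primary p-values.

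Two things are at stake. First, the power statement is attached to no named analysis. It was derived for at least two assessments per child, while the sentence that describes the group comparison speaks of one time point. Second, if the choice is left until data are seen, the promised 0.05 can be neither verified nor guaranteed.

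**Working it through.** **Inputs.** From Sample Size: SD 2.8, correlation 0.3, difference 0.8, 336 analysed, at least two assessments. From section 3 (Randomization): equal allocation, so 168 per arm. From Primary Analysis: two-sided 0.05. Assumed here: the same SD at each visit and the same correlation between every pair of visits.

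**Formulas.** For the mean of *m* visits:

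- variance V = 2.8² × [1 + (m − 1) × 0.3] / m
- SE of the group difference = √(2V / 168)
- power = Φ(0.8 / SE − 1.96)
- difference detectable with 90% power = 3.2415 × SE

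**The plan's own figure (m = 2).** V = 7.84 × 1.3 / 2 = 5.096 and SE = √(10.192 / 168) = 0.2463. Power = Φ(3.248 − 1.96) = 90.1%. The number needed is 3.2415² × 2 × 5.096 / 0.64 = 167.3 per arm, so 168 per arm and 336 in total. The stated 90% reproduces.

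**The candidate tests, 168 per arm**

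| Test (unadjusted) | V | SE | Power for 0.8 | 90% detectable difference |
|---|---|---|---|---|
| One visit (m = 1) | 7.840 | 0.3055 | 74.5% | 0.99 |
| Mean of two visits | 5.096 | 0.2463 | 90.1% | 0.80 |
| Mean of three visits | 4.181 | 0.2231 | 94.8% | 0.72 |

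- The noncentral t distribution gives 74.3% for one visit.
- With all 400 children analysed at one visit, SE = √(2 × 7.84 / 200) = 0.2800 and power = Φ(2.857 − 1.96) = 81.5%. Zero attrition would not restore 90%.
- If baseline SFD also correlates 0.3 with each visit (an assumption; the plan gives no such figure), adjustment takes 7.84 × 0.3² = 0.706 off V. For three visits V = 3.476, SE = 0.2034 and power is 97.6%.

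**Type I error if more than one test could be claimed.** Null z statistics for three visits with correlation r, and their standardized mean, were simulated and each tested at |z| > 1.96. At r = 0.3 a single visit's z correlates √(1.6 / 3) = 0.73 with the mean.

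- Final-visit t-test or three-visit mean: 8.2%.
- 4-month t-test, final-visit t-test or three-visit mean: about 11% (10.4% at r = 0.5, 11.8% at r = 0.2; this range of r is assumed).

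**How often the choice changes the answer.** With a true difference of 0.8 at every visit and r = 0.3, simulation gives a significant three-visit mean with a non-significant final visit in 21% of trials. The reverse occurs in 0.7%.

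**The case against.** The strongest reply is that the intended primary analysis can be inferred. The power basis is a repeated-assessment effect. The outcome is defined over three follow-ups. The mixed model takes SFD as its response and the secondary continuous outcomes follow its pattern, whereas in the t-test sentence SFD is one of seven continuous variables. Baseline comparisons are meant to supply control variables for the treatment-effect analyses, which a bivariate t-test cannot use. The missing-data paragraph for the primary analyses concerns GEE and the mixed model. All of this stands, and it makes a baseline-adjusted mixed model the best-supported reading. It does not settle the point: the model is introduced as an addition, to describe the time-course, and with a treatment-by-time term it yields several treatment effects, none of them designated.

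A reader might infer that the trial is underpowered at 74%. The documents do not support that. The figure needs the t-test to be primary and also to be done at one visit, and the plan states neither.

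A reader might also infer a single-visit SFD test from FeNO, which has only two post-baseline measurements. Those show that a three-visit average cannot apply to FeNO. They do not show how SFD is tested. The sentence is loosely worded and also covers days absent, acute visits and hospitalizations, which accrue over a period.

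Finally, the inflated error rates assume that any of several tests would be claimed at an unadjusted 0.05. The plan commits itself to the opposite; what it lacks is the mechanism.

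**Conclusion.** The gap is real: one primary SFD test is not named, and the time point of the t-test is undefined. The sample size is sound for an averaged contrast, with 90.1% power for two visits and 94.8% for three, unadjusted.

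The adverse figures are conditional. Power of about 74%, with a 90% detectable difference of 0.99 SFD, applies only if the t-test sentence is followed at one visit. Type I error of about 8% or 11% applies only if two or three of the tests could each be claimed as primary, contrary to the family-wise commitment. It should not be read as the trial's expected error rate.

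All figures rest on the plan's SD and correlation and on equal correlation between visits. The power figures also assume 336 children with complete data for the visits averaged. The point should be fixed before analysis, because the choice of test can change the conclusion and the correction needs only wording.

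**What to change.** Name one primary test at two-sided 0.05: the SB-TEAM minus eUC difference in SFD averaged over the 4-month, 6-month and final visits, from the mixed model with treatment, categorical time, treatment-by-time and baseline SFD. Then:

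- make the t-tests descriptive;
- make the per-visit and maintenance contrasts secondary;
- delete the reference to a primary time point, or define it for each outcome;
- state in Sample Size that the 90% power refers to the averaged contrast.

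Naming a final-visit model contrast would also resolve the multiplicity. The average is preferred because it matches both the power basis and the three-visit definition of the outcome.

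The cost is SAP wording only, with no extra children, visits or data; 336 analysed stays adequate. The downside is that claims about a particular visit or about maintenance become secondary.

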We will follow subjects prospectively through the end of the school year, which will vary from between 7-9 months depending on the timing of enrollment for each subject. The preliminary effectiveness of the study will be assessed by telephone interviews with the caregivers, medical record review, and review of school records including, absenteeism, school nurse records (e.g., visits to nurse, medication use at school), and academic performance records. Research assistants, blinded to the subject's group allocation, will conduct telephone calls with caregivers every other month following the initial baseline to collect the follow-up data. At the end of the study year, a home visit will be conducted for the final follow-up assessment at the end of the school year. While the intervention will only last 7-9 months, we may follow subjects for up to 5 years post their enrollment into the study to collect additional outcome measures. These measures may include medical chart review or additional survey assessments with the primary caregiver. If additional surveys are conducted with the caregiver, we will request verbal permission from the caregiver prior to collecting survey data.

Evaluations will be conducted with school health staff members who administered directly observed therapy to children enrolled in the program and/or completed assessments using the web-based system. Paper surveys will be distributed prior to the end of each school year. Respondents will be asked to complete the survey within a 2 week window and return via fax.

Healthcare providers whose patient(s) were enrolled in the program will also be asked to complete a short evaluation asking for feedback on the process. These surveys will be administered on paper and returned via fax and as a web-based survey with an email invitation.

We will also complete semi-structured interviews with participating school health staff and healthcare providers to gather additional information on program acceptability.

5. Measures

The table below summarizes the outcome measures and covariates that will be collected for this study. The table includes how the data will be collected, validated scales/instruments used, and times of administration.

Clinical Outcomes	Measurement Strategy	Time of Administration
Symptom Severity	Caregiver interview, NHLBI guideline-based items Asthma Control Test (ACT)	Baseline, each follow-up, final Baseline, follow-up 2, final

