Health Care Utilization	Caregiver interview – health care utilization survey Review of medical chart and pharmacy records	Baseline, each follow-up Conclusion of Study
Airway Inflammation	Objective measurement: FeNO	Baseline, follow-up 2, final
Pulmonary Function	Spirometry	Baseline, follow-up 2, final
Functional Outcomes		
School Absenteeism	Caregiver interview School record review	Baseline, each follow-up Conclusion of study
Quality of Life	Caregiver interview-PACQLQ	Baseline, each follow-up
Potential Mediators		
Adherence	Caregiver interview- Horne Adherence Scale Pharmacy Data	Baseline, each follow-up End of study
Communication with Providers	Caregiver interview-PEPPI	Baseline, final
Satisfaction with Medical Care	Caregiver interview-PSQ-18	Baseline, final
Independent Variables		
Demographic, Medical Variables	Caregiver interview	Baseline
Caregiver Depression*	Caregiver interview-CES-D	Baseline, final survey
Environmental Allergens	Environmental survey	Baseline
Secondhand Smoke	Caregiver interview Salivary Cotinine measurement	Baseline, each follow-up Baseline, final
Process Evaluation		
Training of School Nurses, CTAs, and Providers	Time to train nurses to deliver DOT with proper inhaler technique, train CTAs for asthma assessments, and providers for reinforcement of guideline based asthma care	Tracking logs for entire study period
Medication Delivery to School	Tracking log of days required to deliver medications to school and home and initiate DOT; both at beginning of the study and for follow-up adjustments	Treatment group only – tracking log
Percent of Days Children Receive Medications via DOT	Nurse medication administration logs	Treatment group only – collected at the end of the school year
Diffusion of Innovations Summary Measures Relative Advantage, Compatibility, Simplicity, Trialability, Observable Results	Semi-structured interview: parents, nurses, administrators, PCPs Perceived Attributes scale ¹² (for school nurses, health aides, and administrators)	At conclusion of study

*All Families will be provided a list of local mental health resources at the beginning of this study.

Fraction of Exhaled Nitric Oxide (FeNO):

Fraction of Exhaled Nitric Oxide (FeNO) measurement is a non-invasive measure of lung inflammation. This inflammation could be caused by many factors including colds, pollutant exposures, and asthma. FeNO will be measured using the NIOX MINO® Airway Inflammation Monitor, an electrochemical hand-

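### Acute visits and hospitalizations are tested by chi-square at one undefined time point; the GEE also planned could recover the loss but is not named as the main analysis and has no follow-up offset

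*Combined protocol and SAP*

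**What the plan says.** Section 11, Primary Analysis, introduces the group comparisons with "To test for differences between the SB-TEAM and eUC groups on clinical and functional outcomes at the primary time point". It assigns t-tests to the continuous outcomes, "and chi-square tests for discrete variables (acute visits, hospitalizations"). The primary time point is singular and is not defined. The only nearby timing statement concerns the primary outcome and lists three follow-ups: "symptom-free days post-intervention (follow-ups at 4 mo, 6mo and final) as the primary outcome".

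Later in the same paragraph the plan adds a second analysis: "Discrete outcomes will be analyzed by fitting Generalized Estimating Equation model". The details are left open: "Appropriate link functions and response probability distributions will be specified".

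On data, the table in section 5 (Measures) collects health care utilization by caregiver interview at baseline and each follow-up, and separately by "Review of medical chart and pharmacy records" at the conclusion of the study. Section 4 (Follow-Up Assessments) spaces the interviews every other month and describes total follow-up as a period "which will vary from between 7-9 months depending on the timing of enrollment for each subject". It also lists medical record review among the sources for judging effectiveness. The only analysis in section 11 that names record review as an input is the cost-effectiveness analysis, where it feeds medical costs together with parent report.

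**The concern.** A score such as the ACT can be compared at a visit because it describes a state. Acute visits and hospitalizations are events spread over months. A comparison at one time point can see only what that assessment covers. A chi-square on children with and without an event also ignores repeat events and takes no account of how long each child was observed.

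The text leaves open the window, the data source, the coding (any event or number of events), the GEE link and distribution, any adjustment for time observed, and which of the two analyses leads. With two analyses and no stated order, they could disagree and the choice could be made after the results are seen.

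What is at stake is a set of secondary outcomes with particular value here. Caregivers know whether their child receives medication at school, even though the telephone interviewers are blinded. Events recorded in charts are therefore a useful check on caregiver-reported symptom-free days. A test that uses a small part of the follow-up could miss a real reduction.

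**Working it through.** **The plan's own power figure.** Section 11 gives power only for symptom-free days: SD 2.8, within-subject correlation 0.3, at least two assessments, difference 0.8, 336 analysed, 90% power. The SD of the mean of two assessments is 2.8 × √((1 + 0.3)/2) = 2.257. Then n per arm = 2 × (1.960 + 1.282)² × 2.257² / 0.8² ≈ 168, which is 336 in total with power 90.1%. The figure reproduces. It says nothing about acute visits or hospitalizations, for which no power, event rate or target effect is given.

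**Share of follow-up in one window.** With interviews two months apart, and assuming that recall matches that spacing, one window leaves out 1 − 2/7 = 71% of a 7-month follow-up and 1 − 2/9 = 78% of a 9-month follow-up.

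**Power of the chi-square, one window against whole follow-up.** From the plan: 168 per arm, taken from the 336. Assumed: whole-follow-up eUC risk p of 10%, 20% or 30%; SB-TEAM risk p/2; events spread evenly over four windows (8 months at 2 months each); yes/no coding; two-sided 0.05.

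- One-window risk = 1 − (1 − risk)^(1/4).
- Power = Φ[(d − 1.96 × SE0)/SE1], where d is the risk difference, SE0 the pooled standard error and SE1 the unpooled one.

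Example at p = 20%. One window: risks 5.43% and 2.60%, d = 0.0283, SE0 = 0.0214, SE1 = 0.0214, so power = Φ(−0.64) = 26%. Whole follow-up: risks 20% and 10%, d = 0.10, SE0 = 0.0390, SE1 = 0.0386, so power = Φ(0.61) = 73%.

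| eUC risk, whole follow-up | One-window risk, eUC / SB-TEAM | Power, one window | Power, whole follow-up |
|---|---|---|---|
| 10% | 2.6% / 1.3% | 14% | 41% |
| 20% | 5.4% / 2.6% | 26% | 73% |
| 30% | 8.5% / 4.0% | 41% | 91% |

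At a 5% whole-follow-up risk, the one-window risk in eUC is 1.27%, or 168 × 0.0127 = 2.1 children expected with an event. That is too few for a chi-square.

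**What the GEE would recover.** Under the same assumptions, a simulation (4,000 runs per scenario) pooled a yes/no outcome over all four windows with robust standard errors. The between-child dispersion k ran from 0 to 2. Power was 40–44%, 76–81% and 94–97% at eUC risks of 10%, 20% and 30%. This is at least about the whole-follow-up chi-square and close to a full-period count model.

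**Sensitivity to a different event model.** Negative binomial counts, mean μ per eUC child over 8 months, k from 0 to 2, rate ratio 0.6, 168 per arm:

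| μ | One-window yes/no | Whole-period yes/no | Whole-period rate model |
|---|---|---|---|
| 0.1 | 9% | 21–25% | 22–25% |
| 0.5 | 24–29% | 42–75% | 58–82% |
| 1 | 34–50% | 45–92% | 73–98% |
| 2 | 42–75% | 41–96% | 82–100% |

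Whole-period yes/no coding leaves 4–11% of events unused at μ = 0.1 and 51–68% at μ = 2. The rate model therefore adds little for rare events and much for frequent or clustered ones.

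**The case against.** The strongest reply is that the chi-square is only a first, bivariate look. The plan follows it with a GEE for discrete outcomes. Utilization is asked at every follow-up, so the GEE can use all interviews, and a child who misses one still contributes the others. Weighted GEE is foreseen if data are missing at random. The simulation supports this reply: pooled over windows, the GEE loses little or nothing against the whole follow-up.

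That stands, and it rules out two stronger conclusions that a reader might draw. One is that the plan as a whole discards most of these events; the other is that it leaves them with almost no power. The low figures belong to the chi-square alone, and only if it uses one interview window. The documents state neither that window nor yes/no coding. Yes/no is the natural inference, since countable outcomes such as days absent are given t-tests, but a chi-square on any event over the school year would also fit the text. A third tempting reading, that nothing is done with the chart data, is also wrong, because they feed the cost analysis.

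Varying follow-up is not by itself a bias either. Randomization should balance enrollment timing between arms on average. The offset matters for withdrawals and for expressing the result as a rate.

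What the reply does not settle is that the GEE is not declared the main analysis, has no offset and has no stated source. If it rests on caregiver interviews, missed interviews matter: the plan itself ties unweighted GEE to data missing completely at random.

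**Conclusion.** The concern holds in a limited form. The one concrete test named for acute visits and hospitalizations is a chi-square at a single undefined time point, which suits outcomes that accumulate over 7 to 9 months poorly. On the one-window reading, its power is roughly one third to under one half of what the whole follow-up gives (14% against 41%, 26% against 73%, 41% against 91%). These figures assume 168 per arm, a halved risk, even spread over four windows and yes/no coding. The documents give no event rates or target effect.

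The planned GEE would recover most of that loss if it pools all follow-up interviews and is the analysis relied on, but the plan says neither. No effectiveness analysis is explicitly assigned to the chart review. Even the best model stays weak if events are rare: 22–25% power at 0.1 events per child with a rate ratio of 0.6. Both outcomes are secondary, and the symptom-free-day analysis and its sample size are unaffected.

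**What to change.** Drop the single-time-point chi-square as the test for these two outcomes. In section 11, state the following:

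- **Outcome:** the number of asthma-related acute visits, and separately of asthma-related hospitalizations, from randomization to the end of the school year. Telemedicine visits scheduled by the protocol are not counted, since only the SB-TEAM arm has them.
- **Source:** chart review.
- **Main analysis:** negative binomial or log-link GEE model with log days observed as offset, reported as a rate ratio with a confidence interval.
- **Supportive analysis:** caregiver report, because charts can miss visits made outside the system.

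The cost is wording in the analysis section. The chart review and the interviews are already planned. The chart abstraction must record event dates and each child's observation period, which the documents do not confirm.
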